### 6.10.2 Performing Adverse Events Assessments

The Investigator is ultimately responsible for assessing and reporting all AEs as outlined in the protocol. The assessment of AEs may be delegated to a medically qualified sub-investigator, trained on this study protocol, who is listed on the FDA Form 1572 or equivalent document, and on the delegation of authority form.

AEs should be volunteered by the subject or solicited from the subject using a standard statement, obtained from examination of the subject at a clinic visit, or from observations of clinically significant laboratory values or special examination abnormal values. If an event assessed by one of the study scales requires intervention, or if in the opinion of the Investigator, it is clinically significant, then it will be reported as an AE.

All AEs are to be assessed and recorded in a timely manner and followed to resolution or until the Investigator determines that there is not an anticipated resolution. Each AE is to be documented with reference to severity, date of occurrence, duration, treatment, and outcome. Furthermore, each AE is to be classified as being serious or non-serious. In addition, the Investigator must assess whether the AE is drug-related or not. Changes in severity of AEs should be documented as one event at the maximum severity that occurred during the study.

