### 6.10.3 Timing

AEs will be captured from the time the subject gives informed consent until the subject completes the study.

Surgical procedures, planned before enrollment of the subject in the study, are not considered AEs if the condition was known before study inclusion. In this case the medical condition should be reported in the subject's medical history.

If a subject experiences the onset of an SAE within 30 days following study completion and in the opinion of the Investigator, that SAE is associated with the study, it will be followed and reported as described in Section [6.10.9.2](#).

If a SAE occurs a PK sample will be taken as soon as possible after the event is reported. If possible, an additional sample should be collected when the SAE has been resolved.

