### 6.10.4 Severity

Adverse events with changes in severity should be documented as one event at the maximum severity.

Intensity	Definition
Mild	Causes transient or mild discomfort ; no limitation of usual activities; no medical intervention required
Moderate	Causes mild to moderate limitation in activity; some limitation of usual activities: no or minimal medical intervention or therapy is required.
Severe	Causes marked limitation in activity; some assistance is usually required; medical intervention or therapy is required; hospitalization is probable.

The term “severe” is used to describe the intensity (severity) of a specific event (as in mild, moderate, or severe); the event itself, however, may be of relatively minor medical significance (such as a severe headache). This is not the same as “serious,” which is based on subject/event outcome or action criteria usually associated with events that pose a threat to a subject’s life or functioning. Seriousness (not severity) serves as a guide for defining regulatory reporting obligations.

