#### 6.10.10 Treatment-Emergent Adverse Events

A TEAE is an AE that either commenced following initiation of study drug or was present prior to the initiation of study drug, but increased in frequency or severity following initiation of treatment, regardless of causality.

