TEAEs are those that started following the first dose of RBP-6000 in this study or were present prior to the first dose of RBP-6000 in this study regardless of causality and increased in severity following administration of RBP-6000 regardless of causality ≤30 days after the last dose of RBP-6000. All AEs which change in severity or relationship to RBP-6000 are assigned a new start date and captured as a new AE. AEs include those events that are ongoing at the time a subject rolls-over from the RB-US-13-0001 but these events will not be considered treatment-emergent.

Sponsor: Indivior Inc.
Protocol no: RB-US-13-0003

Run-In Adverse Events

An AE for the run-in period is an AE that either commenced during the run-in period or was present prior to the initiation of run-in, but increased in severity during run-in, regardless of causality, and prior to the first injection of RBP-6000.

Outcome of Death

Any AE with an outcome of fatal or study discontinuation due to death.

Subjective Opioid Withdrawal Scale Total Score

The SOWS total score is defined as the sum of the responses to the 16 questions as indicated by the subjects on how they feel at the time of completed the questionnaire including anxiousness, yawning, perspiring, teary eyed, runny nose, goosebumps, shaky, hot flushes, cold flushes, bones and muscle achiness, restlessness, nausea, vomiting, muscle twitching, stomach cramps, and feeling like using now. Each answer to a corresponding question is assigned a value between 0 and 4. If 3 or more responses are missing, then a total score will be set to missing. If less than 3 responses are missing, then the total score will be normalized.

Suicidal Ideation Scoring

The suicidal ideation score ranges from 0 to 5 and depends on the answers to the suicidal ideation portion of the eC-SSRS. The score is the maximum suicidal ideation category (in the following order: 1 = wish to be dead, 2 = Non-specific active suicidal thoughts, 3 = active suicidal ideation with any methods (not plan) without intent to act, 4 = active suicidal ideation with some intent to act, without specific plan, and 5 = active suicidal ideation with specific plan and intent) present at the assessment. If all answers to these questions are "No" then the suicidal ideation score is 0.

Suicidal Ideation Intensity Rating:

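### Protocol and SAP give opposite rules for recording an AE whose severity changes, so treatment-emergent status of AEs that began before the first injection can be wrong in either direction

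*SAP*

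**What the plan says.** **Recording rule for sites.** Protocol section 6.10.2: "Changes in severity of AEs should be documented as one event at the maximum severity that occurred during the study". Section 6.10.4 repeats it: "Adverse events with changes in severity should be documented as one event at the maximum severity". Section 6.10.2 also names what is kept for each AE: "Each AE is to be documented with reference to severity, date of occurrence, duration, treatment, and outcome". A date on which the grade changed is not among these items. Under section 6.10.3, "AEs will be captured from the time the subject gives informed consent until the subject completes the study", so run-in AEs are already on file at the first injection.

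**Rule assumed by the analysis.** SAP section 5.0: "All AEs which change in severity or relationship to RBP-6000 are assigned a new start date and captured as a new AE".

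**TEAE definitions.** Protocol section 6.10.10 includes an AE that "was present prior to the initiation of study drug, but increased in frequency or severity following initiation of treatment". SAP section 5.0 keeps a worsening limb ("increased in severity following administration of RBP-6000 regardless of causality") but has no frequency criterion. It adds that AEs ongoing at roll-over from RB-US-13-0001 are recorded, "but these events will not be considered treatment-emergent".

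**Disclosure.** SAP section 1.1 lists six changes from the protocol. None concerns AE recording or the TEAE definition.

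**The concern.** Both documents intend an AE that began before RBP-6000 and then worsened to count as treatment-emergent. To find such an AE, the analysis needs either a separate entry dated at the worsening, or one entry that also holds the earlier grade and the date of change. The protocol asks sites for neither, while the SAP takes the first for granted.

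TEAE incidence heads the primary variables in SAP section 4.1, and protocol section 9.5.1.1 restricts the safety analysis to TEAEs after RBP-6000. Misclassification at the first injection therefore reaches the TEAE, severe-TEAE, related-TEAE and special-interest tables.

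The overlap is plausible. Every subject takes SUBOXONE for 4 to 14 days before injection (3 induction days plus 1 to 11 adjustment days). The label in protocol Appendix 7 lists restlessness, anxiety, piloerection, irritability, rhinorrhea, arthralgia and increased lacrimation as AEs around induction. All seven are among the drug-withdrawal preferred terms in SAP Appendix 2, so that special-interest summary looks the most exposed.

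**Working it through.** The plan gives no figure to reproduce, and no rate of AEs that change after injection, so the check is a trace through the rules.

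**Is one of the texts superseded?** No. SAP section 1.0 says it was built on the protocol dated 04AUG2016, which is Amendment 4, the version reviewed here.

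**Trace.** Take an AE that starts during run-in and is still ongoing at the first injection. Under the SAP it is a TEAE if its entry starts after the first dose (onset limb) or if it was present before and became more severe afterwards (worsening limb).

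| Course of the AE | One entry at worst grade (protocol) | New entry at each change (SAP) | Intended status |
|---|---|---|---|
| Mild in run-in, severe after injection | One severe entry with a run-in start. Onset limb fails; worsening limb cannot be evaluated. Run-in AE at severe grade, not a TEAE. **Wrong** | Mild run-in entry plus severe entry starting after injection. TEAE, severe. Right | TEAE |
| Severe in run-in, mild after injection | One severe entry with a run-in start. Not a TEAE. Right | The second, mild entry starts after injection and meets the onset limb. TEAE. **Wrong** | Not a TEAE |
| Same grade, attribution to RBP-6000 changes after injection | The protocol rule covers severity only. If kept as one entry, not a TEAE. Right | The second entry starts after injection and meets the onset limb. TEAE. **Wrong** | Not a TEAE |
| Mild then severe, both before injection, no worse later | One severe entry with a run-in start. Not a TEAE. Right | Both entries start before injection. Not a TEAE. Right | Not a TEAE |

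The first and fourth rows produce the same single entry: severe, run-in start, ongoing at injection. No programming rule can separate them from the items the protocol requires, so a table that captures the first row must also count the fourth.

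**What softens the effect.** Under SAP section 9.6.1.1, subjects are counted once per system organ class and preferred term. A subject with another TEAE under the same preferred term still counts there, though possibly at too low a grade. A missed event also remains in the run-in tables and in the listing of all AEs. The overview table does report numbers of events, and splitting changes those directly.

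**The case against.** The strongest defence is that the SAP sentence describes the incoming data. It is in the present tense, and the SAP cites a CRF dated 22SEP2016, later than the protocol. Sites enter data under CRF completion guidelines, which are not among the documents. If those guidelines split entries, no worsened AE is lost and the protocol wording is simply out of date. This stands as a limit: the loss is conditional. It does not remove the problem, because under splitting the second and third rows of the trace go wrong instead, and the two documents still conflict.

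Four stronger readings are tempting and are not supported:

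- **TEAE incidence is biased downward.** That holds only for single-entry data. The SAP splits on any change, improvement included, which pushes the count upward.
- **Roll-over AEs never count, even if they worsen.** The exclusion covers AEs ongoing at roll-over, but the sentence before it makes any change in severity a new AE. A carried-over AE that worsens could therefore be a new entry with a post-injection start. The text is ambiguous and does not amount to a blanket exclusion.
- **Dozens of subjects are affected.** Assuming that 5% to 10% of about 600 subjects have such a worsening would give 0.05 × 600 = 30 to 0.10 × 600 = 60, but no document supplies that rate. Subjects must also reach COWS ≤ 12 and craving ≤ 20 mm before injection, and scale findings become AEs only if they need intervention or are judged clinically significant.
- **Sites cannot be compared.** No between-site AE comparison is planned.

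It is also fair to object to changing the site instruction now. Data to 12 August 2016 have already been analysed at the interim, and a late change would itself mix the two recording practices.

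**Conclusion.** The conflict is real, lies in current text and is undisclosed in SAP section 1.1. It makes the treatment-emergent status of pre-injection AEs unreliable under either recording rule: worsened run-in AEs are missed with single entries, and improved or re-attributed ones can be counted with split entries. The direction and size of the net error cannot be derived from the documents, and CRF guidelines not supplied here decide which case applies. The conclusion assumes that sites had no means of dating a change in grade beyond what the protocol names.

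A smaller, separate point also holds: the protocol's frequency criterion has disappeared from the SAP definition without being listed, although protocol section 9.1 says departures from its analyses will be set out in the SAP. The items required for each AE do not include frequency, so the criterion may not have been derivable, which is a reason to state its removal. This should be settled before the final tables are run.

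**What to change.** Make the changes in the SAP, since much of the data is already collected:

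1. State which recording rule the collected data follow, and whether it held throughout the study, and list it in section 1.1 as a difference from protocol sections 6.10.2 and 6.10.4.
2. Define the worsening limb as an increase in severity after the first injection relative to the last severity before it. With split entries, link those belonging to one event, so that an improvement or a change in relationship alone does not create a TEAE.
3. State explicitly that a roll-over AE that worsens after injection is assessed under the same rule.
4. List the removal of the frequency criterion in section 1.1.
5. If the data are single entries, add a sensitivity TEAE table, overall and by maximum severity. It should count AEs ongoing at first injection whose maximum severity cannot be dated before it, and be labelled as an upper bound.

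The cost is a few sentences, some linking of entries if they were split, and at most one extra table. That table may overcount, because it will include AEs that never worsened after injection; the upper-bound label is there for that reason.

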9.6 Primary Safety Analyses

9.6.1 Incidence of Adverse Events

9.6.1.1 Adverse Events

Imputation of AE (for determination of TEAE only) and concomitant medication start and stop dates:

Start Date: If only 'day' is missing, and the month and year are not the same as the month of first dose, then impute day with '01'. Otherwise, if the month and year are the same as the first dose date, use the first dose date. If 'day' and 'month' are missing, and 'year' is not missing, then impute month and day with month and day of the first dose date (assuming same 'year'). If 'day' and 'month' are missing and 'year' is not missing and is not the same year as first dose date, then impute with '01' for both 'day' and 'month'. If the start date is completely missing, it will be set to the first dose date.

Stop Date: If only 'day' is missing, impute day with last day of the month. If 'day' and 'month' are missing, and 'year' is not missing, then impute month with '12' and day with '31' (or date of study discontinuation/completion if earlier than 12-31 and year is the same as the year of discontinuation). If the stop date is completely missing, it will be set to the date of study discontinuation/completion. A stop date will not be applied to ongoing AEs or ongoing medications.

Treatment-related Adverse Events

Any AE with a relationship to study treatment of 'Related' or missing will be considered a treatment-related AE as determined by the Investigator.

A summary of treatment-emergent AEs will be presented for the Safety Analysis Set and the Run-In Safety Analysis Set, including the number of events reported, the number and percentage of subjects reporting at least one AE, the number and percentage of subjects with the following:

- Related AEs
- SAEs
- Related SAEs
- AEs with an outcome of death
- Severe TEAEs
- AEs leading to discontinuation

A breakdown of the number and percentage of subjects reporting each AE categorized by SOC and PT coded according to the MedDRA dictionary version 17.1 will be presented for the Run-In period using the Run-In Safety Analysis Set and for the open label RBP-6000 treatment period using the Safety Analysis Set. Note that counting will be by subject not event and subjects are only counted once within each SOC or PT. AEs/TEAEs related to SUBOXONE/study treatment will be presented in a similar manner.

A further tabulation of events experienced by $\geq 5\%$ of subjects by SOC and PT will be presented for the Safety Analysis Set.

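### SAP 5.0 lets a run-in adverse event that eases, or is only re-attributed, after the first RBP-6000 injection become a treatment-emergent event

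*SAP*

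**What the plan says.** The TEAE paragraph of SAP 5.0 contains four rules that interact.

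- Limb 1, on start date: "TEAEs are those that started following the first dose of RBP-6000 in this study". No worsening is required.
- Limb 2, for an AE already present before the first injection: it counts if it "increased in severity following administration of RBP-6000 regardless of causality ≤30 days after the last dose of RBP-6000".
- New-record rule: "All AEs which change in severity or relationship to RBP-6000 are assigned a new start date and captured as a new AE". It covers severity and relationship, and it does not say that the change must be for the worse.
- One exemption: "AEs include those events that are ongoing at the time a subject rolls-over from the RB-US-13-0001 but these events will not be considered treatment-emergent". AEs that began in this study's SUBOXONE run-in are not covered.

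Run-in AEs have their own definition in the same section: "An AE for the run-in period is an AE that either commenced during the run-in period or was present prior to the initiation of run-in".

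Protocol 6.10.10 counts a pre-existing AE only if it "was present prior to the initiation of study drug, but increased in frequency or severity following initiation of treatment". Protocol 6.10.2 and 6.10.4 both tell sites to document an AE whose severity changes as a single event at its worst grade. SAP 1.1, which lists the changes from the protocol, mentions neither the new-record rule nor the dropped frequency criterion.

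On counting, SAP 9.6.1.1 plans an overview "including the number of events reported, the number and percentage of subjects reporting at least one AE". Its SOC and PT tables count each subject once per term, and its severity tables use the subject's most severe event in the term.

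**The concern.** The new-record rule supplies a post-injection start date, and limb 1 asks only for a post-injection start date. Limb 2, the one place where the SAP asks for worsening, is therefore bypassed. An AE that was moderate in the run-in and becomes mild after Day 1 qualifies as a TEAE because it improved. An AE whose severity never changes qualifies if the investigator revises its relationship to RBP-6000. Because SAP 9.6.1.1 treats a related or missing relationship as related, such a record can also enter the treatment-related tables.

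TEAE incidence is the first variable listed in SAP 4.1. The overview, the SOC/PT tables, the related-AE tables, the table of events in at least 5% of subjects and the drug-withdrawal table (SAP 9.6.1.5) all draw on the same flag. The Appendix 2 term list for that last table includes anxiety, insomnia, nausea, chills and hyperhidrosis, which are plausible complaints during induction. One illness could appear in both the run-in and the open-label tables. The error is not purely cautious either: a severe run-in AE that eases can enter the TEAE tables as a mild event, which adds to incidence and dilutes apparent severity.

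**Working it through.** The plan states no figure for this point, so there is nothing to reproduce. The check applies the wording to constructed AE courses.

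**Inputs.** The limbs and the new-record rule come from SAP 5.0. The comparator combines Protocol 6.10.2 and 6.10.4 (one event) with 6.10.10 (worsening required for a pre-existing AE). First injection = Day 1. The courses are invented to exercise the rules and say nothing about frequency.

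**Formulas.**
- SAP wording: TEAE events = number of records with a start date on or after Day 1. For an on-treatment AE this is the number of changes + 1. For a run-in AE it is the number of changes after the injection.
- Comparator: 1 if the AE starts on treatment, or if it began in the run-in and its severity later exceeds its pre-injection severity; otherwise 0.
- Subjects: 1 if the subject has at least one TEAE in the term.

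| Course | Events, SAP | Events, comparator | Subjects, SAP | Subjects, comparator |
|---|---|---|---|---|
| A. Run-in moderate, eases to mild on Day 10 | 1 | 0 | 1 | 0 |
| B. Run-in mild, re-attributed on Day 10 | 1 | 0 | 1 | 0 |
| C. Run-in mild, worsens to moderate on Day 10 | 1 | 1 | 1 | 1 |
| D. Run-in moderate, no change | 0 | 0 | 0 | 0 |
| E. Starts Day 5: mild, moderate, severe, moderate, mild | 4 + 1 = 5 | 1 | 1 | 1 |
| F. Starts Day 5 mild, re-attributed on Day 9 | 1 + 1 = 2 | 1 | 1 | 1 |
| Total | 10 | 3 | 5 | 3 |

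**Where the excess comes from.** Events: 10 − 3 = 7, of which A and B give 1 + 1 = 2, E gives 5 − 1 = 4 and F gives 2 − 1 = 1. Subjects: 5 − 3 = 2, entirely from A and B. Splitting an AE that began on treatment therefore never adds a subject to a term. Only a run-in AE still ongoing at Day 1 can do that.

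Course C also shows that, once records are split, limb 2 has no work left for run-in AEs: the worsened record already qualifies through limb 1.

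**A built-in limit.** Protocol 6.10.4 has three grades. A mild AE cannot step down to a lower grade, so the easing route needs an AE that is moderate or severe when the first injection is given.

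**The case against.** **Limb 2 could govern.** A run-in AE was present before the first dose, so the specific limb might be read as controlling it, with the next sentence a recording convention. This is good evidence that worsening was the intended test. It does not settle the matter, because the sentence assigns a new start date and says the record is captured as a new AE, and limb 1 works on start date.

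**Sites may never have split on severity.** Protocol 6.10.2 and 6.10.4 tell them not to. If they complied, the easing route produces no records. This stands: the CRF is not among the documents. But the protocol's rule does not cover changes of relationship, and the SAP describes splitting as how AEs are captured.

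**Re-attribution should be rare.** Protocol 6.10.5 reserves the related category for AEs that other factors cannot reasonably explain, which is hard to argue for an AE that began before any RBP-6000 was given in this study. This stands as a limit on frequency.

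**Over-counting errs towards caution, and every AE is listed.** This is partly true, subject to the dilution of severity noted above.

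**Stronger readings that the documents do not support.**
- A reader might infer that splitting inflates all the AE tables. The SOC/PT tables count subjects once, and the severity tables use the worst event.
- A reader might infer a percentage of subjects affected. The extra subjects in a term would be at most N × p × q, with N about 600, p the share with a run-in AE ongoing at Day 1 and q the share of those that ease or are re-attributed. The documents give neither p nor q. The label table in Protocol Appendix 7 cannot stand in for p: withdrawal syndrome in 25.2% on SUBOXONE tablets (37.4% on placebo) covers a whole 4-week study, and is not the share ongoing on a given day.
- Enrollment requires COWS of 12 or less (Protocol 4.4), which Protocol 6.11.3 grades as mild at most. Subjects in moderate or worse withdrawal on that scale do not reach the injection, although individual AEs may still be graded higher.
- The share of subjects with any TEAE changes only for those with no other TEAE. In the single-dose study, 46 of 51 (90.2%) had at least one. If that rate held here, which is an assumption, this line would move little.

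**Conclusion.** The point holds as a defect of wording. Applied as written, SAP 5.0 makes a run-in AE treatment-emergent when it eases or is only re-attributed after the first injection. That contradicts the SAP's own limb 2 and Protocol 6.10.10. It also departs from Protocol 6.10.2 and 6.10.4 without being listed in SAP 1.1.

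The reach is limited. Subject-level incidence is affected only through run-in AEs ongoing at Day 1. Repeat splitting of on-treatment AEs affects only the event count in the overview and the listings. How many records are involved cannot be computed from the documents, since it depends on whether sites followed the protocol or the SAP when an AE changed. The conclusion assumes only that the TEAE flag will be derived from the start dates that the SAP prescribes. It does not claim that false TEAEs are in the data.

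**What to change.** Before the final database lock, revise the TEAE paragraph of SAP 5.0 to say the following.

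1. An AE present before the first RBP-6000 injection is treatment-emergent only if, after that injection, it rises above its severity at the time of the injection or becomes more frequent, in line with Protocol 6.10.10.
2. A record created only by a fall in severity or a change of relationship keeps the start date and TEAE status of the original AE.
3. For the event count, records of the same AE count once, at the maximum post-injection severity, and as related if any post-injection record is related or missing. Records are joined by a CRF link or, failing that, by the same preferred term with contiguous dates.
4. All records stay in the listings.

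Two choices guard against losing real events. The comparator is severity at the injection, not the worst severity beforehand; otherwise an AE that was severe early in the run-in, mild at the injection and severe again afterwards would be dropped. The any-record rule for relationship prevents an event once called related from leaving the related tables.

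SAP 5.0 should also be reconciled with Protocol 6.10.2 and 6.10.4, and any remaining departure listed in SAP 1.1. The cost is one SAP paragraph and a little extra programming for the linking flag. If the CRF carries no link between records, the preferred-term and date rule serves instead.

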## 6.10 Adverse Events Assessments

### 6.10.1 Definition

In accordance with ICH and US FDA guidance, any untoward medical occurrence incurred by a subject that occurs after the first study-related procedure to the completion of the last EOS/ET visit or start of treatment on the INDV-6000-301 study and is associated with the use of the drug, regardless of the presence of causal relationship, is a reportable AE. AEs that are ongoing at the time a subject rolls-over from the RB-US-13-0001 study will be recorded in the eCRF.

Abnormal results of diagnostic procedures, including laboratory test abnormalities, are considered AEs if they:

- Result in discontinuation from the study,
- Require treatment or any other therapeutic intervention,
- Require further diagnostic evaluation (excluding a repetition of the same procedure to confirm the abnormality), or

- Are associated with clinical signs or symptoms that would have a significant clinical impact, as determined by the Investigator.

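### SAP 5.0 bars adverse events ongoing at roll-over from treatment-emergent status with no exception for worsening, so roll-over and de novo subjects can be counted under different rules

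*SAP*

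**What the plan says.** SAP 5.0 builds the TEAE definition in four steps:

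1. New onset: "TEAEs are those that started following the first dose of RBP-6000 in this study".
2. Worsening: an AE already present also counts if it "increased in severity following administration of RBP-6000 regardless of causality ≤30 days after the last dose of RBP-6000". No subject type is named.
3. Record rule: "All AEs which change in severity or relationship to RBP-6000 are assigned a new start date and captured as a new AE".
4. Exclusion: "AEs include those events that are ongoing at the time a subject rolls-over from the RB-US-13-0001 but these events will not be considered treatment-emergent". Nothing is said about worsening.

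Protocol 6.10.10 also counts an AE that "was present prior to the initiation of study drug, but increased in frequency or severity following initiation of treatment, regardless of causality", and makes no exception for roll-over subjects. Protocol 6.10.1 expects carried-over events to be in the data: "AEs that are ongoing at the time a subject rolls-over from the RB-US-13-0001 study will be recorded in the eCRF". Protocol 6.10.2 and 6.10.4 tell sites to keep an AE whose severity changes as a single event, graded at its worst. SAP 1.1, which lists the departures from the protocol, mentions neither the roll-over exclusion nor the new-record rule.

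SAP 4.1 puts TEAE incidence first among the primary variables. SAP 9.0 presents summaries by subject type unless stated otherwise.

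**The concern.** The exclusion is unqualified, names roll-over subjects only, and sits in the definition behind the first primary variable. If it reaches events that worsen after the first injection in this study, the same clinical course is a TEAE in a de novo subject and not in a roll-over subject. The two groups appear in adjacent columns, so a difference between them could come from the definition.

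The tables that depend on TEAE status are the TEAE overview, the related and severe TEAE tables (SAP 9.6.1.1) and the special-interest tables (SAP 9.6.1.5 to 9.6.1.11, including hepatic and injection-site events). Roll-over subjects are about 300 of the planned 600. Some will have had RBP-6000 in RB-US-13-0001, and SAP 3.3 counts exposure across both studies towards the one-year target. Worsening of an existing event on further dosing is something a long-term safety study should show.

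**Working it through.** The documents give no figure to reproduce, so the check is mainly one of logic.

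**What the exclusion can change.** Take an AE ongoing at roll-over that stays the same. It did not start after the first dose in this study and did not increase in severity, so it fails both parts of the definition without the last sentence. Two minor groups aside, the sentence can alter only the status of events that worsened. The minor groups are records whose missing start date is imputed to the first dose date (SAP 9.6.1.1) and records re-dated only because the assessed relationship changed. For worsening, the sentence is therefore either redundant or it removes worsened events.

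**A pre-existing AE that worsens after the first injection: is it a TEAE?** Two things decide this: how a severity change is recorded, and what the exclusion covers.

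| Record rule | Exclusion covers | Roll-over | De novo |
|---|---|---|---|
| SAP: new record | Carried-over record only | Yes | Yes |
| SAP: new record | Whole event | No | Yes |
| Protocol: single record | Carried-over record only | No | Yes |
| Protocol: single record | Whole event | No | Yes |

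- In row 1 the worsened record has a start date after the dose and meets the new-onset part.
- In rows 3 and 4 there is no second record. The worsening part brings the de novo event in, and the exclusion blocks the roll-over event. These rows assume that the data show severity rose after the first dose. The documents do not say whether the eCRF keeps the earlier grade.

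Subject types are treated differently in three of the four combinations. They are treated alike in the SAP's own sequence (row 1).

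**Comparison inside SAP 5.0.** The Run-In AE definition counts a pre-existing AE that became more severe during run-in, with no roll-over exclusion. On the wider reading of the exclusion, worsening of a carried-over event would count under SUBOXONE but not under RBP-6000.

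**Illustrative size.** Affected subjects = N × p × w.

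- N = 300 roll-over subjects (protocol 3.1, SAP 3.0).
- p = share with an AE ongoing at roll-over; assumed 10% to 50%.
- w = share of those whose event worsens; assumed 5% to 20%.

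| p | w | Subjects | Points of roll-over column (÷ 300) | Points of total (÷ 600) |
|---|---|---|---|---|
| 0.10 | 0.05 | 300 × 0.10 × 0.05 = 1.5 | 0.5 | 0.25 |
| 0.30 | 0.10 | 300 × 0.30 × 0.10 = 9 | 3 | 1.5 |
| 0.50 | 0.20 | 300 × 0.50 × 0.20 = 30 | 10 | 5 |

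Each subject counts once in the any-TEAE row, and many may have another TEAE, so these are upper bounds for that row. In row 1 of the first table the effect is zero.

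**The case against.** The strongest reply is to read SAP 5.0 in order. A carried-over AE that worsens after injection becomes a new AE with a post-dose date. That new record was not ongoing at roll-over, so the exclusion does not reach it, and it qualifies as new onset. The last sentence then only keeps unchanged events from the earlier study out of the counts, and both subject types are treated alike.

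This is a fair reading, and it limits the point. A reader might infer that the SAP rules carried-over events out for good, even when they worsen, and that the tables do miss real worsening. The text does not say so. Other tempting inferences also go too far:

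- **Serious events.** SAP 9.6.1.2 tabulates SAEs without a treatment-emergent restriction and lists all of them for screened subjects. The SAE row of the TEAE overview and the restriction to TEAEs in protocol 9.5.1.1 leave some doubt, but loss from the serious tables is not established.
- **Liver and injection-site findings.** Laboratory threshold counts and shift tables (SAP 9.6.2) and injection-site grading (SAP 9.6.4.3) do not depend on TEAE status.
- **Complete loss.** SAP 9.6.1.1 lists all AEs, including those that are not TEAEs.
- **Half the population.** About 300 is the number of roll-over subjects, not the number affected. Protocol 4.3 also lets investigators exclude roll-over subjects whose earlier AEs could compromise safety.

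What the reply does not remove is the ambiguity. The exclusion speaks of events, not records, and nothing in it limits it to unchanged events. The reply also depends on a second record that protocol 6.10.2 and 6.10.4 tell sites not to create.

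**Conclusion.** The point holds as an undeclared conflict, not as a settled rule that discards worsening. The exclusion contradicts the worsening part of its own definition and protocol 6.10.10, and the SAP and protocol disagree on how a change in severity is recorded. If the single-record rule governs the data, or if the exclusion covers the whole event, a worsened pre-existing AE is a TEAE in a de novo subject and not in a roll-over subject. The TEAE overview, related, severe and special-interest tables would then use different rules by subject type.

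The size cannot be derived from the documents. The 1.5 to 30 subjects rest entirely on the assumed shares, are an upper bound for the any-TEAE row, and fall to zero under the new-record reading. Because the definition feeds the first primary variable and the correction is small, it should be made before the final tables are run.

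**What to change.** Replace the last sentence of the SAP 5.0 definition with: *AEs ongoing at roll-over from RB-US-13-0001 are not treatment-emergent unless they increase in severity after the first RBP-6000 dose in this study, whether captured as one record or as a new record.*

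Then:

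- apply the same worsening rule to de novo and roll-over subjects;
- reconcile the SAP's new-record rule with protocol 6.10.2 and 6.10.4, state which one the eCRF followed, and match the derivation to it;
- either restore the protocol's criterion of increased frequency for both subject types, or list its removal in SAP 1.1. The SAP now drops it for everyone without saying so.

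The cost is a sentence in SAP 5.0, entries in SAP 1.1 and a check of the TEAE flag. If severity changes were kept as single records, someone must also confirm that the timing of worsening can be recovered. Roll-over TEAE counts may rise slightly.
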